5.2 Trial Treatment(s)

The treatment to be used in this trial is outlined below in [Table 2](#).

Table 2 Trial Treatment

Study Treatment Name	Dosage Formulation	Unit Dose Strength(s)	Dosage Level(s)	Route of Administration	Sourcing
Pembrolizumab (MK-3475)	Solution for infusion	100 mg per vial	200 mg Q3W	IV infusion	Central

Abbreviations: IV = intravenous; N/A = not applicable; Q3W = every 3 weeks; QD = every day.

Trial treatment should begin on the day of treatment allocation/randomization or as close as possible to the date on which the subject is allocated/assigned.

The investigator shall take responsibility for and shall take all steps to maintain appropriate records and ensure appropriate supply, storage, handling, distribution and usage of trial treatments in accordance with the protocol and any applicable laws and regulations.

5.2.1 Dose Selection/Modification

5.2.1.1 Dose Selection (Preparation)

The rationale for selection of doses to be used in this trial is provided in Section 4.0 – Background & Rationale. There are no specific calculations or evaluations required to be performed in order to administer the proper dose to each subject.

5.2.1.2 Dose Modification (Escalation/Titration/Other)

5.2.1.2.1 Pembrolizumab

Dose modification and toxicity management for immune-related AEs associated with pembrolizumab

AEs associated with pembrolizumab exposure may represent an immunologic etiology. These immune-related AEs (irAEs) may occur shortly after the first dose or several months after the last dose of pembrolizumab treatment and may affect more than one body system simultaneously. Therefore, early recognition and initiation of treatment is critical to reduce complications. Based on existing clinical trial data, most irAEs were reversible and could be managed with interruptions of pembrolizumab, administration of corticosteroids, and/or other supportive care. For suspected irAEs, ensure adequate evaluation to confirm etiology or exclude other causes. Additional procedures or tests such as bronchoscopy, endoscopy, or skin biopsy may be included as part of the evaluation. Based on the severity of irAEs, withhold or permanently discontinue pembrolizumab and administer corticosteroids. Dose modification and toxicity management guidelines for irAEs associated with pembrolizumab are provided in [Table 3](#).

Table 3 Dose Modification and Treatment Discontinuation Guidelines for Immune-related Adverse Events Associated with Pembrolizumab

General instructions:				

 1. Corticosteroid taper should be initiated upon AE improving to Grade 1 or less and continue to taper over at least 4 weeks. 2. For situations where pembrolizumab has been withheld, pembrolizumab can be resumed after AE has been reduced to Grade 1 or 0 and corticosteroid has been tapered. Pembrolizumab should be permanently discontinued if AE does not resolve within 12 weeks of last dose or corticosteroids cannot be reduced to ≤ 10 mg prednisone or equivalent per day within 12 weeks. 3. For severe and life-threatening irAEs, IV corticosteroid should be initiated first followed by oral steroid. Other immunosuppressive treatment should be initiated if irAEs cannot be controlled by corticosteroids. 				
irAEs	Toxicity grade or conditions (NCI CTCAE v4.0)	Action taken to pembrolizumab	irAE management with corticosteroid and/or other therapies	Monitor and follow-up
Pneumonitis	Grade 2	Withhold	
 • Administer corticosteroids (initial dose of 1-2 mg/kg prednisone or equivalent) followed by taper 	
 • Monitor participants for signs and symptoms of pneumonitis • Evaluate participants with suspected pneumonitis with radiographic imaging and initiate corticosteroid treatment • Add prophylactic antibiotics for opportunistic infections
	Grade 3 or 4, or recurrent Grade 2	Permanently discontinue		
Diarrhea / Colitis	Grade 2 or 3	Withhold	
 • Administer corticosteroids (initial dose of 1-2 mg/kg prednisone or equivalent) followed by taper 	
 • Monitor participants for signs and symptoms of enterocolitis (ie, diarrhea, abdominal pain, blood or mucus in stool with or without fever) and of bowel perforation (ie, peritoneal signs and ileus). • Participants with \geqGrade 2 diarrhea suspecting colitis should consider GI consultation and performing endoscopy to rule out colitis. • Participants with diarrhea/colitis should be advised to drink liberal quantities of clear fluids. If sufficient oral fluid intake is not feasible, fluid and electrolytes should be substituted via IV infusion.
	Grade 4	Permanently discontinue		

irAEs	Toxicity grade or conditions (NCI CTCAE v4.0)	Action taken to pembrolizumab	irAE management with corticosteroid and/or other therapies	Monitor and follow-up
AST / ALT elevation or Increased bilirubin	Grade 2	Withhold	
 Administer corticosteroids (initial dose of 0.5-1 mg/kg prednisone or equivalent) followed by taper 	
 Monitor with liver function tests (consider weekly or more frequently until liver enzyme value returned to baseline or is stable)
	Grade 3 or 4	Permanently discontinue	
 Administer corticosteroids (initial dose of 1-2 mg/kg prednisone or equivalent) followed by taper 	
Type 1 diabetes mellitus (T1DM) or Hyperglycemia	Newly onset T1DM or Grade 3 or 4 hyperglycemia associated with evidence of β -cell failure	Withhold	
 Initiate insulin replacement therapy for participants with T1DM Administer anti-hyperglycemic in participants with hyperglycemia 	
 Monitor participants for hyperglycemia or other signs and symptoms of diabetes.
Hypophysitis	Grade 2	Withhold	
 Administer corticosteroids and initiate hormonal replacements as clinically indicated. 	
 Monitor for signs and symptoms of hypophysitis (including hypopituitarism and adrenal insufficiency)
	Grade 3 or 4	Withhold or permanently discontinue ¹		
Hyperthyroidism	Grade 2	Continue	
 Treat with non-selective beta-blockers (eg, propranolol) or thionamides as appropriate 	
 Monitor for signs and symptoms of thyroid disorders.
	Grade 3 or 4	Withhold or permanently discontinue ¹		
Hypothyroidism	Grade 2-4	Continue	
 Initiate thyroid replacement hormones (eg, levothyroxine or liothyronine) per standard of care 	
 Monitor for signs and symptoms of thyroid disorders.
Nephritis and Renal dysfunction	Grade 2	Withhold	
 Administer corticosteroids (prednisone 1-2 mg/kg or equivalent) followed by taper. 	
 Monitor changes of renal function
	Grade 3 or 4	Permanently discontinue		

irAEs	Toxicity grade or conditions (NCI CTCAE v4.0)	Action taken to pembrolizumab	irAE management with corticosteroid and/or other therapies	Monitor and follow-up
Myocarditis	Grade 1 or 2	Withhold	
 Based on severity of AE administer corticosteroids 	
 Ensure adequate evaluation to confirm etiology and/or exclude other causes
	Grade 3 or 4	Permanently discontinue		
All other irAEs	Intolerable/persistent Grade 2	Withhold	
 Based on type and severity of AE administer corticosteroids 	
 Ensure adequate evaluation to confirm etiology and/or exclude other causes
	Grade 3	Withhold or discontinue based on the type of event. Events that require discontinuation include and not limited to: Guillain-Barré Syndrome, encephalitis		
	Grade 4 or recurrent Grade 3	Permanently discontinue		

Abbreviations: AE = adverse event; ALT = alanine aminotransferase; AST = aspartate aminotransferase; CTCAE = Common Terminology Criteria for Adverse Events; GI = gastrointestinal; irAE = immune-related adverse event; IV = intravenous; NCI = National Cancer Institute; T1DM = type 1 diabetes mellitus.
 
1. Withhold or permanently discontinue pembrolizumab is at the discretion of the investigator or treating physician.
 
NOTE: For participants with Grade 3 or 4 immune-related endocrinopathy where withhold of pembrolizumab is required, pembrolizumab may be resumed when AE resolves to \leqGrade 2 and is controlled with hormonal replacement therapy or achieved metabolic control (in case of T1DM).
				

Dose modification and toxicity management of infusion-reactions related to pembrolizumab

Pembrolizumab may cause severe or life threatening infusion-reactions including severe hypersensitivity or anaphylaxis. Signs and symptoms usually develop during or shortly after drug infusion and generally resolve completely within 24 hours of completion of infusion. Dose modification and toxicity management guidelines on pembrolizumab associated infusion reaction are provided in [Table 4](#).

Table 4 Pembrolizumab Infusion Reaction Dose Modification and Treatment Guidelines

NCI CTCAE Grade	Treatment	Premedication at Subsequent Dosing

Grade 1 Mild reaction; infusion interruption not indicated; intervention not indicated
	
Increase monitoring of vital signs as medically indicated until the subject is deemed medically stable in the opinion of the investigator.
	
None


Grade 2 Requires therapy or infusion interruption but responds promptly to symptomatic treatment (e.g., antihistamines, NSAIDs, narcotics, IV fluids); prophylactic medications indicated for ≤24 hrs
	
Stop Infusion. Additional appropriate medical therapy may include but is not limited to: IV fluids Antihistamines NSAIDs Acetaminophen Narcotics Increase monitoring of vital signs as medically indicated until the subject is deemed medically stable in the opinion of the investigator. If symptoms resolve within 1 hour of stopping drug infusion, the infusion may be restarted at 50% of the original infusion rate (e.g. from 100 mL/hr to 50 mL/hr). Otherwise dosing will be held until symptoms resolve and the subject should be premedicated for the next scheduled dose. Subjects who develop Grade 2 toxicity despite adequate premedication should be permanently discontinued from further study drug treatment
	
Subject may be premedicated 1.5 h (±30 minutes) prior to infusion of pembrolizumab with: Diphenhydramine 50 mg PO (or equivalent dose of antihistamine). Acetaminophen 500-1000 mg PO (or equivalent dose of analgesic).

NCI CTCAE Grade	Treatment	Premedication at Subsequent Dosing

Grades 3 or 4 Grade 3: Prolonged (i.e., not rapidly responsive to symptomatic medication and/or brief interruption of infusion); recurrence of symptoms following initial improvement; hospitalization indicated for other clinical sequelae (e.g., renal impairment, pulmonary infiltrates) Grade 4: Life-threatening; pressor or ventilatory support indicated
	
Stop Infusion. Additional appropriate medical therapy may include but is not limited to: Epinephrine** IV fluids Antihistamines NSAIDs Acetaminophen Narcotics Oxygen Pressors Corticosteroids Increase monitoring of vital signs as medically indicated until the subject is deemed medically stable in the opinion of the investigator. Hospitalization may be indicated. **In cases of anaphylaxis, epinephrine should be used immediately. Subject is permanently discontinued from further study drug treatment.
	
No subsequent dosing


Abbreviations: CTCAE = Common Terminology Criteria for Adverse Events; IV = intravenous; NCI = National Cancer Institute; NSAIDs = nonsteroidal anti-inflammatory drugs; PO = by mouth Appropriate resuscitation equipment should be available at the bedside and a physician readily available during the period of drug administration. For further information, please refer to the CTCAE v4.0 at http://ctep.cancer.gov
		

Other allowed dose interruption for pembrolizumab

Pembrolizumab may be interrupted for situations other than treatment-related AEs such as medical / surgical events or logistical reasons not related to study therapy. Subjects should be placed back on study therapy within 3 weeks of the scheduled interruption, unless otherwise discussed with the Sponsor. The reason for interruption should be documented in the subject's study record.

5.2.2 Timing of Dose Administration

5.2.2.1 Pembrolizumab

The first infusion should be administered on the day of treatment allocation or as close as possible to the date on which the subject is allocated, ie, ≤7 days. Pembrolizumab should be administered on Day 1 of each 3 week cycle after all procedures/assessments have been completed as detailed on the Trial Flow Chart (Section 6). After the first cycle, trial treatment may be administered up to 3 days before or after the scheduled Day 1 of the cycle due to administrative reasons.

Details pertaining to the preparation and administration of pembrolizumab are provided in the Pharmacy Manual.

5.2.3 Trial Blinding/Masking

This is an open-label trial; therefore, the Sponsor, investigator and subject will know the treatment administered.

5.3 Randomization or Treatment Allocation

Treatment allocation will occur centrally using an interactive voice response system/integrated web response system (IVRS/IWRS). All eligible subjects will be allocated to receive pembrolizumab 200 mg Q3W as monotherapy. Subjects enrolled in Cohorts 4 and 5 will remain on their current stable SOC dose of enzalutamide therapy during pembrolizumab monotherapy. Enzalutamide will not be supplied by the sponsor.

5.4 Stratification

All eligible subjects will be enrolled into one of the cohorts in this study based on treatment history, PD-L1 status for Cohorts 1 and 2 only, and RECIST 1.1 measurability.

No additional stratification based on age, sex or other characteristics will be used in this trial.

5.5 Concomitant Medications/Vaccinations (Allowed & Prohibited)

Medications or vaccinations specifically prohibited in the exclusion criteria are not allowed during the ongoing trial. If there is a clinical indication for any medication or vaccination specifically prohibited during the trial, discontinuation from trial therapy or vaccination may be required. The investigator should discuss any questions regarding this with the Sponsor Clinical Director. The final decision on any supportive therapy or vaccination rests with the investigator and/or the subject's primary physician. However, the decision to continue the subject on trial therapy or vaccination schedule requires the mutual agreement of the investigator, the Sponsor and the subject.

5.5.1 Acceptable Concomitant Medications

All treatments that the investigator considers necessary for a subject's welfare may be administered at the discretion of the investigator in keeping with the community standards of medical care. All concomitant medication will be recorded on the case report form (CRF) including all prescription, over-the-counter (OTC), herbal supplements, and IV medications and fluids. If changes occur during the trial period, documentation of drug dosage, frequency, route, and date may also be included on the CRF. Subject may remain on anti-coagulation therapy as long as the PT or PTT is within therapeutic range of the intended use of anticoagulants.

For Cohorts 4 and 5, the use of enzalutamide will be recorded on the CRF. If dose modification of enzalutamide is required during the trial period, documentation of dosage should also be included on the CRF.

5.5.2 Prohibited Concomitant Medications

Subjects are prohibited from receiving the following therapies during the Screening and Treatment Phase (including retreatment for post-complete response relapse) of this trial:

- Antineoplastic systemic chemotherapy or biological therapy
- GM-CSF
- Immunotherapy not specified in this protocol
- Chemotherapy not specified in this protocol
- Investigational agents other than pembrolizumab
- Radiation therapy

Note: Palliative localized radiation therapy to a site of pre-existing disease may be permitted while on study after consultation with Sponsor. The radiation treatment field may not include a target or measurable lesion by RECIST 1.1. Pre-existing treatment with Radium-223 dichloride is allowed so long as the last dose has been administered no fewer than 4 weeks from the first dose of trial drug.

- Live vaccines within 30 days prior to the first dose of trial treatment and while participating in the trial. Examples of live vaccines include, but are not limited to, the following: measles, mumps, rubella, chickenpox, yellow fever, rabies, Bacillus Calmette-Guerin (BCG), and oral typhoid vaccine. Seasonal influenza vaccines for injection are generally killed virus vaccines and are allowed; however intranasal influenza vaccines (e.g., FluMist[®]) are live attenuated vaccines, and are not allowed.

Note: Any licensed COVID-19 vaccine (including for Emergency Use) in a particular country is allowed in the study as long as they are mRNA vaccines, adenoviral vaccines, or inactivated vaccines. These vaccines will be treated just as any other concomitant therapy. Investigational vaccines (ie, those not licensed or approved for Emergency Use) are not allowed.

- Systemic glucocorticoids for any purpose other than to modulate symptoms from an AE of suspected immunologic etiology. The use of physiologic doses of corticosteroids may be approved after consultation with the Sponsor.

Note: Inhaled steroids for management of asthma are permitted.

Note: Use of prophylactic corticosteroids to avoid allergic reactions (e.g., to IV contrast dye) is permitted.

Note: Treatment with palliative prednisone such as 10 mg daily or corticosteroids equivalent in the manner used to treat men with prostate cancer is permitted.

Note: Physiologic doses of corticosteroids for adrenal insufficiency are permitted.

Subjects who, in the assessment by the investigator and after consultation with the Sponsor, require the use of any of the aforementioned treatments for clinical management should be removed from the trial. Subjects may receive other medications that the investigator deems to be medically necessary.

The Exclusion Criteria describe other medications which are prohibited in this trial.

There are no prohibited therapies during the Post-Treatment Follow-up Phase. Subjects must be discontinued from the active follow-up phase if they begin a non-trial treatment for their underlying disease.

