Adverse events (AEs) will be monitored throughout the trial and graded in severity according to the guidelines outlined in the National Cancer Institute (NCI) Common Terminology Criteria for Adverse Events (CTCAE) version 4.0 (See Appendix 12.6). Treatment with pembrolizumab will continue until documented confirmed disease progression, unacceptable AEs, intercurrent illness that prevents further administration of treatment, Investigator's decision to discontinue the subject, subject discontinuation from the study, noncompliance with trial treatment or procedure requirements, subject receives 35 administrations of pembrolizumab (approximately 2 years), or administrative reasons requiring the cessation of treatment.

Subjects who attain an Investigator-determined confirmed complete response (CR) may receive up to 35 infusions of pembrolizumab. Subjects who discontinue after 35 infusions for reasons other than disease progression or intolerability, or who discontinue after attaining a CR (and had at least 8 administrations of pembrolizumab and at least 2 treatments beyond initial CR) may be eligible for up to 17 additional infusions (approximately 1 year) of

pembrolizumab after they have experienced radiographic disease progression. The decision to retreat will be at the discretion of the Investigator only if no cancer treatment was administered since the last dose of pembrolizumab, the subject still meets the safety parameters listed in the Inclusion/Exclusion criteria, and the trial remains open (refer to Section 7.1.5.2. for further details).

[figure not shown]
After the end of treatment, each subject will be followed for 30 days for AE monitoring (serious AEs [SAEs] will be collected for 90 days after the end of treatment or 30 days after the end of treatment if the subject initiates new anticancer therapy, whichever is earlier). Subjects who discontinue treatment for reasons other than disease progression will stay on study and continue to undergo study-related disease assessments until disease progression, initiation of a non-study cancer treatment, withdrawal of consent, or becoming lost to follow-up. All subjects will be followed by telephone contact for overall survival (OS) until death, withdrawal of consent or the end of the study, whichever comes first.

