5.8 Subject Withdrawal/Discontinuation Criteria

5.8.1 Discontinuation of Treatment

Discontinuation of treatment does not represent withdrawal from the trial.

As certain data on clinical events beyond treatment discontinuation may be important to the study, they must be collected through the subject's last scheduled follow-up, even if the subject has discontinued treatment. Therefore, all subjects who discontinue trial treatment prior to completion of the treatment will still continue to participate in the trial as specified in Section 6.0 - Trial Flow Chart and Section 7.1.5.3 – Post Treatment.

Subjects may discontinue treatment at any time for any reason or be dropped from treatment at the discretion of the investigator should any untoward effect occur. In addition, a subject may be discontinued from treatment by the investigator or the Sponsor if treatment is inappropriate, the trial plan is violated, or for administrative and/or other safety reasons. Specific details regarding procedures to be performed at treatment discontinuation are provided in Section 7.1.4 – Other Procedures.

A subject must be discontinued from treatment but continue to be monitored in the trial for any of the following reasons:

- The subject or subject's legally acceptable representative requests to discontinue treatment.
- The subject has a medical condition or personal circumstance which, in the opinion of the investigator and/or sponsor, placed the subject at unnecessary risk from continued administration of study drug.
- The subject has a positive urine drug screen at any time during the course of the trial.
- Documented disease progression as assessed by the investigator using PCWG3-modified RECIST 1.1 guidelines (Section 7.1.2.6.1 – Initial Tumor Imaging). Two consecutive assessments are needed for disease progression. Clinical deterioration will not be considered progression.
- Unacceptable adverse experiences as described in Section 5.2.1.2 – Dose Modification (Escalation/Titration/Other) and Section 5.6.1 – Supportive Care Guidelines
- Intercurrent illness that prevents further administration of treatment
- Noncompliance with trial treatment or procedure requirements
- Administrative reasons

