5.8.2 Withdrawal from the Trial

Subjects may withdraw from the trial at any time for any reason. If a subject withdraws from the trial, they will no longer receive treatment or be followed at scheduled protocol visits.

A subject must be withdrawn from the trial if:

- The subject or subject's legally acceptable representative withdraws consent from the trial.
- The subject is lost to follow-up.

Specific details regarding procedures to be performed at the time of withdrawal from the trial including specific details regarding withdrawal from Future Biomedical Research are outlined in Section 7.1.4 – Other Procedures.

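### Protocol Section 5.5.2 removes from the trial subjects who need a prohibited therapy. This contradicts the follow-up rules elsewhere and, if applied literally, can informatively censor OS and three Cohort 4/5 endpoints

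*Protocol*

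**What the plan says.** Section 5.5.2 of the protocol lists therapies prohibited during screening and treatment: chemotherapy, biological therapy, other immunotherapy, GM-CSF, other investigational agents, radiation, live vaccines, and systemic glucocorticoids, with stated exceptions for some. It then says that subjects who, in the investigator's assessment and after consultation with the Sponsor, "require the use of any of the aforementioned treatments for clinical management should be removed from the trial".

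Other sections treat leaving treatment and leaving the trial as different things:

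- Section 5.5, on a clinical need for a prohibited medication: "discontinuation from trial therapy or vaccination may be required".
- Section 5.8.1: "Discontinuation of treatment does not represent withdrawal from the trial". On data about clinical events after treatment stops: "they must be collected through the subject's last scheduled follow-up, even if the subject has discontinued treatment".
- Section 5.8.2, on leaving the trial: "If a subject withdraws from the trial, they will no longer receive treatment or be followed at scheduled protocol visits". The mandatory reasons are two: "The subject or subject's legally acceptable representative withdraws consent from the trial", or the subject is lost to follow-up.
- Section 2.1: "All subjects will be followed by telephone contact for overall survival (OS) until death, withdrawal of consent or the end of the study".
- Sections 7.1.1.5.4 and 7.1.5.3.1: a subject who starts new anticancer therapy moves into survival follow-up.

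Protocol Table 9 and SAP Table 3 censor OS at the last date known alive. They apply the same rule to time to cytotoxic chemotherapy, time to new anticancer therapy and time to first skeletal-related event in Cohorts 4 and 5.

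**The concern.** Section 5.5.2 uses trial-removal wording where the follow-up rules use treatment-discontinuation wording, and prohibited therapy is not among the Section 5.8.2 reasons. The only exit from the trial that the protocol describes is Section 5.8.2, after which subjects are no longer followed at scheduled visits.

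A site that reads 5.5.2 this way would stop following a subject because of a treatment need. Where that need reflects worsening disease, the censoring depends on prognosis. Kaplan-Meier estimates for endpoints censored at the last date known alive would then be too favourable.

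**Working it through.** **Reading the sections side by side**

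| Question | Section 5.5.2 | Elsewhere in the protocol |
|---|---|---|
| What stops when a prohibited therapy is needed? | Participation in the trial | Trial therapy, and only possibly (5.5) |
| Is it a mandatory reason to leave the trial? | Yes, as worded | Not listed (5.8.2) |
| Does data collection continue? | Not if removal means withdrawal (5.8.2) | Yes, after treatment stops (5.8.1) |
| Is survival followed? | Not stated | All subjects (2.1), including those starting new anticancer therapy (7.1.1.5.4, 7.1.5.3.1) |

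**Which analyses are exposed**

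- *ORR*: missing response data count as non-response (Protocol 8.6.1), so it is largely unaffected.
- *rPFS and DOR*: SAP Tables 1 and 2 already censor at new anticancer therapy. For that trigger 5.5.2 adds nothing. Other triggers could add some censoring.
- *Imaging and PSA*: in post-treatment follow-up these already end at new anticancer treatment (flow chart 6.1 footnote d; 7.1.2.6.3; 7.1.2.8).
- *OS*: exposed if survival contact ends.
- *Cohort 4/5 times to chemotherapy, new therapy and first skeletal-related event*: if the triggering therapy is given and recorded, that endpoint's event is already captured. Three cases remain: removal on need, before the therapy starts; later events of the other endpoints; and removal for an unrelated trigger. A contact that records vital status only would move the censoring date forward without showing whether such an event had occurred.

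**Possible size for OS (illustration only)**

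The documents give no removal rate and no hazard after removal. Assumptions: exponential death time with a 12-month median if nobody were removed, so h = ln 2 / 12 = 0.0578 per month; hazard kh after removal; all survival contact lost at removal. In these models Kaplan-Meier with censoring at removal estimates exp(-ht), a median of 12.0 months. With removal rate r, true survival is

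G(t; r) = exp(-(h+r)t) + [r / (h + r - kh)] × [exp(-kht) - exp(-(h+r)t)].

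- *Model A*: every subject is at risk of removal. A share p is removed before death, so r = hp/(1-p) and S = G.
- *Model B*: a fraction f is destined for removal after a mean of 3 months, so r = 1/3 and S = (1-f)exp(-ht) + f·G. The share actually removed is f·r/(r+h), for example 0.20 × 0.3333/0.3911 = 17%.

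Example, model A with p = 20% and k = 2: r = 0.25h, so S = (4/3)exp(-1.25ht) - (1/3)exp(-2ht). At 12 months ht = 0.693, giving 0.5606 - 0.0833 = 47.7%, against an estimate of 50%. S falls to 0.5 at 11.28 months.

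True median in months, with the overstatement in brackets:

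| Scenario | k = 1 | k = 1.5 | k = 2 | k = 3 |
|---|---|---|---|---|
| A, 10% removed | 12.00 (0) | 11.80 (0.20) | 11.65 (0.35) | 11.44 (0.56) |
| A, 20% removed | 12.00 (0) | 11.58 (0.42) | 11.28 (0.72) | 10.86 (1.14) |
| A, 30% removed | 12.00 (0) | 11.34 (0.66) | 10.87 (1.13) | 10.25 (1.75) |
| B, 5% destined (4% removed) | 12.00 (0) | 11.81 (0.19) | 11.66 (0.34) | 11.47 (0.53) |
| B, 20% destined (17% removed) | 12.00 (0) | 11.25 (0.75) | 10.73 (1.27) | 10.03 (1.97) |
| B, 30% destined (26% removed) | 12.00 (0) | 10.91 (1.09) | 10.17 (1.83) | 9.21 (2.79) |

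A simulation of model B (200,000 subjects per scenario, 24-month cut-off) agrees: with 20% destined and k = 3 the true median is 10.06 and the censored estimate 12.03. With k = 1 there is no bias, but about 4% (5% destined) to 16% (20% destined) of deaths go unobserved.

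**The case against.** The strongest reply is that removal is not defined and the more specific rules settle the matter. Section 2.1 follows all subjects for survival. Sections 7.1.1.5.4 and 7.1.5.3.1 send subjects who start new anticancer therapy to survival follow-up. Section 5.5.2 itself goes on to a post-treatment follow-up phase with no prohibited therapies, and says that subjects starting non-trial treatment leave active follow-up. The survival-status requests (flow chart 6.1 footnote i; 7.1.5.4) reach all participants without a scheduled contact, except recorded deaths. The Sponsor is consulted before any removal.

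Much of this stands, and it rules out several stronger statements that a reader might infer:

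- *That survival and safety data are lost.* No section prescribes this; it is a risk under one reading. At withdrawal, End-of-Treatment activities are done and adverse events then present are followed (7.1.4.1). Section 7.2.3.1 keeps SAE reporting for 90 days, or 30 days after new anticancer therapy if earlier, and requires related SAEs at any time. What remains is weaker detection of new SAEs once visits stop.
- *That chemotherapy before confirmed progression costs the 90-day SAE window, imaging or rPFS.* New anticancer therapy already shortens the first and ends or censors the others.
- *That follow-up ends exactly at the Cohort 4/5 events.* An event that was given and recorded is captured.
- *That bone radiotherapy always triggers removal.* Localized palliative radiation to pre-existing disease may be permitted (5.5.2, 5.6.2).
- *That those removed are all doing badly.* GM-CSF and live vaccines are also triggers.

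The reply does not dispose of the point. The specific survival rules cover new anticancer therapy or confirmed progression. For glucocorticoids outside the exceptions, GM-CSF or live vaccines, only the general rules in 2.1 and 5.8.1 oppose removal, and 5.5.2 contradicts them. The 5.5.2 trigger is also need, which can precede the start of therapy. Survival-status requests are at the Sponsor's option.

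**Conclusion.** The contradiction is certain from the text; the consequence is conditional. If a site applies 5.5.2 literally, scheduled follow-up ends, and OS and the three Cohort 4/5 endpoints can be informatively censored. The survival-status requests and the SAE rules limit this risk but do not remove it. Primary ORR is largely unaffected, and no hypothesis test depends on the affected endpoints.

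The size of any OS bias is unknown. It is zero if the hazard does not rise after removal. With an assumed 12-month median, hazards 1.5 to 3 times higher and every survival contact lost, it is roughly 0.2 to 2 months in most of the scenarios shown, and 2.8 in the most extreme. A reader might take these as expected months of bias. The documents do not support that, because neither the removal rate nor the later hazard is given and several rules keep survival contact going. The correction should still be made, because the sentence is an explicit instruction to sites.

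**What to change.** Reconcile Section 5.5.2 with Sections 5.5, 5.8.1, 5.8.2, 2.1, 7.1.1.5.4 and 7.1.5.3.1. State in 5.5.2 that subjects who need a prohibited therapy remain in the trial for survival, subsequent-therapy, skeletal-event and safety follow-up, and for disease assessment where the flow chart still requires it, unless consent is withdrawn. Subjects already removed under this sentence remain due survival contact under Section 7.1.5.4 if their consent stands.

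Whether trial treatment stops in this situation is for the sponsor to reconcile between 5.5, 5.5.2 and 5.8.1; no clinical rule is proposed here.

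The cost is one sentence in an amendment and no new visits, since survival and subsequent-therapy contacts are already in the flow chart. Skeletal events have no row of their own there, so the sentence should name the contact at which they are recorded.
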